The primary outcomes is nocturnal plasma FFA levels. The main independent variable is OSA versus CPAP exposure during sleep. Since FFA are measured multiple times per subject per night, we will perform mixed linear model analysis using condition as a fixed factor and subject ID as a random factor. Sleep physiology that is measured on a continuous basis will be condensed into 30 minute bins to create a parallel data structure with metabolic parameters. As a secondary analysis, we will also examine whether there are patient-specific (“static”) determinants of FFA level during sleep such as age, sex, or body mass index and whether these variables interact with sleep (“dynamic”) variables such as OSA severity. We hypothesize that OSA exposure increases FFA, compared to CPAP. We will then examine whether sleep physiology (e.g. AHI, arousals, heart rate) is dynamically associated with FFA, and whether urine catecholamine levels are associated with increases in FFA. For variables measured once (RHI, morning lipid profile) or averaged (e.g. nocturnal FFA level) we will perform one-way ANOVA for comparisons. We will also compare sleep physiology between the 3 nights, examining variables such as apnea hypopnea index, metrics of hypoxia, and sleep architecture/duration. Data analysis will be performed with a biostatistician and described under the “Study Statistics” section.

b. Study duration and number of study visits required of research participants.

Each study subject will make two overnight visits to the sleep lab. Subjects will be screened with an initial telephone interview. During this screening, only information necessary to assess eligibility for the study will be collected, or information voluntarily provided by the patient to initiate or maintain correspondence. Subjects without any of the self-reported exclusionary criteria will be scheduled for a face-to-face visit for further screening. At this visit, eligibility for

participation in the study protocols will be confirmed. Urine screening for pregnancy in women of child-bearing age will also be performed.

c. Blinding, including justification for blinding or not blinding the trial, if applicable.

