We will include adults of all races ≥ 20 and ≤ 75 years old, with a history of mild to severe OSA (AHI or RDI > 10). They must also own a CPAP machine and report the ability to tolerate sleeping with or without CPAP during the night.

Exclusion Criteria:

1. Uncontrolled hypertension with systolic blood pressure > 170 or diastolic blood pressure > 110
2. Congestive heart failure
3. Use of, clonidine, or nicotinic acid medication
4. Diabetes requiring the use of insulin
5. Pregnancy, by urine testing in women of child-bearing age

6. Patients with a prior history of falling asleep while driving, involved in a near-miss or motor vehicle accident, or and those in high-risk occupations such as commercial drivers or pilots.
7. Hemoglobin < 10 g/dL on point of care screening.

6. Drugs/ Substances/ Devices

- a. The rationale for choosing the drug and dose or for choosing the device to be used.

During CPAP withdrawal nights (both at home and in the lab) we will use NDS as a CPAP placebo. NDS may improve snoring but have no treatment value for OSA[6]. By including NDS as a placebo, we will avoid potential confounding such as anxiety caused by stopping CPAP.

- b. Justification and safety information if non-FDA approved drugs without an IND will be administered.
N/A

Study Statistics

The overall analysis plan has been presented in section 4, “Data Analysis and Anticipated Outcomes”. In this section we briefly address the statistical methods to be used for analysis separated by specific aim:

Specific Aim 1: To examine whether OSA, elicited by CPAP withdrawal, causes lipolysis and cardio-metabolic dysfunction.

Primary outcome: FFA level, comparing between CPAP and OSA nights, analyzed using linear mixed effect models.
Independent variable: CPAP/OSA exposure.

Specific Aim 2: To examine factors associated with lipolysis during sleep.

Primary outcome: FFA level

Independent variables: OSA severity (AHI, arousal index, heart rate, urine catecholamines), Patient factors (age, sex, body mass index/fat distribution).

These analyses are primarily designed to understand the heterogeneity of lipolysis during CPAP withdrawal.

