- *Sex-specific effects:* This will be assessed by (1) comparing mean change in FFA level during CPAP withdrawal between men and women (unpaired T-test); (2) modeling mean FFA level as a function of sex (as well as sex x BMI interactions) in multivariable regression. We hypothesize that men will exhibit greater OSA-induced FFA elevation than women, with or without adjustment for OSA severity and fat distribution.
- *Effects of OSA severity or sympathetic activation:* We will apply linear mixed models with FFA as the outcome, OSA severity or SNS variables (e.g. AHI, ODI, arousal index, HR, urine catecholamines) as fixed factors and subject ID as the random effects variable. Iterative time lags will be used to account for potential delayed effects of dynamic variables. We hypothesize that plasma FFA level will be independently associated with AHI, arousals from sleep, HR elevation, or urine catecholamine level.
- *Identification of robust “responders”:* We will examine FFA elevation as a dichotomous outcome, defining “FFA responders” as those who exhibit Δ FFA $\geq 10\%$ during CPAP withdrawal (subject to change depending on the distribution of responses; the 10% threshold is based on a median increase in nocturnal FFA of $\sim 8.9\%$ in our preliminary data). OSA severity, sleep architecture, sex, age, and fat mass will be compared between responders and non-responders.
- *Identification of potential “downstream” effects of FFA elevation.* We will test the association between nocturnal FFA profile and other cardiometabolic outcomes (e.g. morning OGTT, endothelial function). Multivariable regression will be used to adjust for potential confounders such as age, sex, and BMI.
- *Identification of potential circulating genetic/epigenetic changes.* An exploratory aim of this study is to examine effects of CPAP withdrawal on peripheral blood mononuclear cell (PBMC) gene expression. We will utilize real-time polymerase chain reaction (RT-PCR) arrays (Qiagen MAP Kinase RT2 Profiler and Human Toll-Like Receptor (TLR) Signaling Pathway RT2 Profiler PCR Arrays, Qiagen, Valencia, CA) to characterize gene changes that result from nocturnal hypoxemia.

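### The Aim 2 responder analysis compares predictors across a near-median, movable split of ΔFFA, and no continuous ΔFFA model is written for fat mass, age or sleep architecture

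*Combined protocol and SAP*

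**What the plan says.** Under Study Statistics, the stated outcome for Specific Aim 2 is FFA level, and the purpose is given as: "These analyses are primarily designed to understand the heterogeneity of lipolysis during CPAP withdrawal". Five bullets follow.

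- **Sex.** Mean change in FFA is compared between men and women by an unpaired t-test. Mean FFA level is also regressed on sex, with a sex-by-BMI interaction.
- **OSA severity and sympathetic activation.** "We will apply linear mixed models with FFA as the outcome", with AHI, ODI, arousal index, heart rate and urine catecholamines as fixed factors, subject as random effect, and time lags.
- **Responders.** "We will examine FFA elevation as a dichotomous outcome". A responder has ΔFFA of at least 10%, a threshold based on a pilot median rise of about 8.9% and "subject to change depending on the distribution of responses". Then: "OSA severity, sleep architecture, sex, age, and fat mass will be compared between responders and non-responders". No test is named, and no rule says how the cut would move.
- The last two bullets concern downstream cardiometabolic effects and gene expression.

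Section 4, Data Analysis and Anticipated Outcomes, adds a secondary analysis of "determinants of FFA level during sleep such as age, sex, or body mass index and whether these variables interact with sleep" variables such as OSA severity. It also relates sleep physiology to FFA over the night and asks "whether urine catecholamine levels are associated with increases in FFA". The DEXA paragraph of section 4 names fat mass as a predictor of FFA elevation but gives no model.

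**The concern.** Aim 2 asks who shows a larger FFA rise when CPAP is withdrawn, so the quantity of interest is a within-person change. A main effect of age or fat mass on FFA level shows who has high FFA on both nights, not who rises more off CPAP. That question needs ΔFFA as the outcome, or a term letting the night effect vary with the predictor.

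For fat mass, age and sleep architecture neither is written out. The one specified analysis with the FFA rise itself as outcome is the split, which treats a rise just above the cut like a very large one, and a rise just below it like a fall. A moderate association that the same subjects could show on the continuous scale may be missed.

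The movable cut adds a smaller problem: without a rule, a reader of the results cannot tell on what basis the groups were formed.

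**Working it through.** **1. The plan's own sample size.** From the Sample Size paragraph, ΔFFA is 0.047 ± 0.04 mmol/l in 13 men and 0.021 ± 0.04 mmol/l in 7 women.

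- d = (0.047 − 0.021)/0.04 = 0.65.
- A two-sided 5% two-sample t-test with 80% power needs 38.14 per group, so 39 per group and 78 in all.
- 78/0.85 = 91.8, so 92 enrolled.

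Both stated figures reproduce. They rest on the continuous sex comparison, not on the split. n = 78 is used below.

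**2. Where the cut falls.** The documents give no baseline FFA, so this step is an assumption.

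- Pooled pilot mean ΔFFA = (13 × 0.047 + 7 × 0.021)/20 = 0.0379 mmol/l.
- If this corresponds to the 8.9% median, baseline FFA is 0.0379/0.089 = 0.426 mmol/l and a 10% rise is 0.0426 mmol/l.
- SD including the sex difference = √(0.04² + 0.65 × 0.35 × 0.026²) = 0.0419.
- z = (0.0426 − 0.0379)/0.0419 = 0.11, so about 46% would be responders under normality. The cut is near the median.

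**3. Information kept.** For normal ΔFFA cut at c with responder share p, a predictor's correlation shrinks by the factor φ(c)/√(p(1 − p)). Its square is the relative efficiency.

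| Responder share | Factor | Efficiency | 78 subjects act like |
|---|---|---|---|
| 50% | 0.798 | 0.637 (= 2/π) | 49.7 |
| 45% | 0.796 | 0.633 | 49.4 |
| 30% | 0.759 | 0.576 | 44.9 |

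**4. Power at n = 78.** Power ≈ Φ(atanh(r)·√75 − 1.96), two-sided 5%.

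- Continuous, r = 0.3127: 0.3235 × 8.660 − 1.96 = 0.84, giving 80%.
- Median split, r = 0.3127 × 0.798 = 0.2495: 0.2549 × 8.660 − 1.96 = 0.25, giving 60% (61% by simulation).
- 30% share: 55%.

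The correlation detectable with 80% power rises from 0.31 to about 0.39.

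**5. Dependence on the shape of ΔFFA.** Simulated power (%) at r = 0.25/0.30/0.35, with the split analysed by a two-sample t-test of the predictor across the observed median:

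| Distribution of ΔFFA | Continuous (Pearson) | Median split |
|---|---|---|
| Normal | 61/77/89 | 42/57/71 |
| Skewed (skewness 1) | 58/75/87 | 43/57/71 |
| Heavy-tailed (t, 5 df) | 61/78/89 | 56/72/84 |

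In the heavy-tailed case a rank analysis gives 66/81/92.

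**6. False positives.** With normal data and no association, rejection is 5.0% on the continuous scale and 5.2% with a cut at the observed median.

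**7. Coverage elsewhere in the plan.**

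| Factor | Other planned analysis | What is not written |
|---|---|---|
| Sex | t-test of continuous change | nothing needed here |
| OSA severity | FFA mixed model with AHI, ODI and arousal index | little; if fitted over both nights, it largely captures the change |
| Age | FFA level, with interaction with OSA severity | ΔFFA model or age-by-condition term |
| Sleep architecture | sleep physiology against FFA within the night, in part | ΔFFA model or condition term |
| Fat mass | named as predictor of FFA elevation; fat distribution listed for FFA level | any ΔFFA model form |

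**The case against.** A reader might infer that Aim 2 searches for determinants only through the split, or that OSA severity shares the gap equally. The documents do not support either reading. Aim 2's outcome is continuous FFA level, and the responder bullet is the third of five, after two bullets that keep FFA continuous. OSA severity has an explicit mixed model. The planned interaction of age, sex or BMI with OSA severity comes close to asking whether age modifies the rise. Section 4 also uses the term sleep physiology in a way that includes sleep architecture when it compares nights, so its analysis of sleep physiology against FFA may reach that factor too. All of this stands and narrows the point.

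The size of the loss can also be challenged. The correlations, the distribution and the test are assumptions, and heavy tails shrink the loss to about 5 points. A responder share near 30% would need a baseline around 0.60 mmol/l, at which the pilot mean rise would be 0.0379/0.60 = 6.3%. That fits the stated 8.9% median poorly, so the 45–50% rows are the more relevant ones.

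Finally, this is a self-described pilot with a brief statistics section, and a responder table is a reasonable description. That is fair, but it does not supply a continuous analysis for the three remaining factors.

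**Conclusion.** The point holds as a minor one, confined to the responder bullet. It is firmest for fat mass, partial for age and sleep architecture, and weak for OSA severity. Under approximate normality and a responder share of 45–50%, the split discards about 36–37% of the information and lowers power from about 80% to about 60% for a predictor correlated 0.31 with ΔFFA at n = 78. Moderate skewness changes this little; heavy tails reduce it to about 5 points.

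A reader might also infer that the movable cut inflates false positives. The documents tie the move to the distribution of responses, not to the predictors, and a cut at the observed median keeps the error rate at about 5%. What is missing is the rule and its timing. The primary comparison, the sex test and the sample size are unaffected.

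**What to change.** In the responder bullet:

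1. Make the inferential analysis continuous. Either regress ΔFFA on each listed factor singly and then jointly, or add condition-by-predictor terms to the FFA mixed model. Add a rank-based sensitivity analysis.
2. State whether ΔFFA is in percent, as in this bullet, or in mmol/l, as in the Sample Size paragraph.
3. Keep the responder comparison as a descriptive table.
4. If the cut may move, set it from the pooled ΔFFA distribution, for example at the observed median, before the predictors are examined.

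This takes a few sentences and no new data. The cost is a less simple two-group summary. The joint model also loses some power: at r = 0.25/0.30/0.35 it has 57/75/88% with five uncorrelated predictors and 50/66/80% if they correlate 0.3 with each other. That is why the single-predictor results should be reported beside it.

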**Metabolic Impact of Intermittent CPAP
Consent Form**

Johns Hopkins IRB # NA_00086830

Document Date: 06/23/2021

NCT02824263

Johns Hopkins Medicine - eForm A

- Use the section headings to write the eForm A, inserting the appropriate material in each. If a section is not applicable, leave heading in and insert N/A.
- When submitting eForm A (new or revised), enter the date submitted to the field at the top of eForm A.

1. Abstract

- a. Provide no more than a one page research abstract briefly stating the problem, the research hypothesis, and the importance of the research.

Obstructive sleep apnea (OSA) causes repetitive airway closure during sleep, and is associated with metabolic and cardiovascular dysfunction. The manner in which OSA affects metabolism during sleep is not well studied, but could reveal mechanisms by which OSA promotes cardiovascular diseases. We have previously shown that OSA increases free fatty acids (FFA) in subjects with congestive heart failure (CHF)[1]. Excessive plasma FFA, even when transiently elevated, can induce metabolic and vascular dysfunction[2]. Hence, nocturnal FFA elevations could be responsible for the cardio-metabolic consequences of OSA.

In this study, we will examine if OSA increases FFA in healthy (non-CHF) subjects, and the effects of treating OSA with continuous positive airway pressure (CPAP). We will also determine whether changes in nocturnal FFA caused by OSA are associated with adverse vascular endothelial function and altered glucose metabolism. This pilot study is needed before determining whether FFA levels in OSA constitute a biomarker of cardio-metabolic risk.

2. Objectives (include all primary and secondary objectives)

Specific Aim 1: To examine whether OSA, elicited by CPAP withdrawal, causes lipolysis and cardio-metabolic dysfunction.

We hypothesize that OSA activates lipolysis during sleep, resulting in high levels of plasma glycerol and FFA, which are lowered by CPAP. We also hypothesize that CPAP withdrawal will impair glucose tolerance and endothelial function, and increase glucose production during sleep.

Specific Aim 2: To examine factors associated with lipolysis during sleep.

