We hypothesize that patient specific and sleep-specific factors influence nocturnal lipolysis. Patient factors may include age, sex, or body mass index (BMI). Sleep-specific factors may include OSA severity and/or OSA-induced sympathetic activation, elapsed time, or sleep stage. Additional outcomes of interest are effects of OSA, CPAP on circulating genetic/epigenetic changes.

3. Background (briefly describe pre-clinical and clinical data, current experience with procedures, drug or device, and any other relevant information to justify the research)

OSA induces repetitive upper airway closure during sleep, and affects 24% of middle aged men and 9% of women in the United States[3]. Several studies suggest that OSA may induce cardio-metabolic complications such as insulin resistance, endothelial dysfunction, and dyslipidemia[4] culminating in cardiovascular disease and death[5]. Unfortunately, it remains unclear what mediates detrimental outcomes in OSA. We have shown that OSA causes rapid FFA elevations during sleep in heart failure subjects, which can be prevented by supplemental oxygen [1]. We speculate that stimulation of the sympathetic nervous system by OSA and intermittent hypoxia cause lipolysis, leading to excessive FFA mobilization from adipose tissue.

It is not known whether OSA causes surges of FFA in non-CHF patients, and whether CPAP can abolish the increase. It is also unclear which patient-related or sleep apnea features predict nocturnal FFA elevations, and

whether FFA elevations from OSA are associated acutely with detrimental physiologic changes. In subjects with a history of OSA, we will examine nocturnal FFA in the presence or absence of therapeutic CPAP. We hypothesize that CPAP withdrawal leads to increases in nocturnal FFA. We will also determine whether morning endothelial function and glucose tolerance correlate with nocturnal FFA changes.

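### The objective on downstream effects asks about within-person FFA change, but its only written analysis names no change score, condition term or subject effect

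*Combined protocol and SAP*

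**What the plan says.** The objective is stated twice, both times as change. Section 1 (Abstract) asks whether "changes in nocturnal FFA caused by OSA are associated with adverse vascular endothelial function and altered glucose metabolism". Section 3 (Background) says: "We will also determine whether morning endothelial function and glucose tolerance correlate with nocturnal FFA changes".

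The analysis is one bullet under Specific Aim 2 in Study Statistics. Its heading is "Identification of potential “downstream” effects of FFA elevation", and its text is: "We will test the association between nocturnal FFA profile and other cardiometabolic outcomes (e.g. morning OGTT, endothelial function", followed by "Multivariable regression will be used to adjust for potential confounders such as age, sex, and BMI". Study Statistics refers back to section 4 for the overall plan. The data-analysis text there gives no model linking FFA to these outcomes. For variables measured once or averaged it offers a one-way ANOVA between conditions.

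Other bullets in the same list are more specific. The OSA-severity bullet enters its predictors "as fixed factors and subject ID as the random effects variable". The sex bullet compares mean change in FFA, and the responder bullet defines response by Δ FFA.

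On design, section 4 has each subject studied on a CPAP night and a nasal-strip (NDS) night in random order. Section 9 confirms that the OGTT and EndoPAT follow each of the two visits. On eligibility, the only diabetes exclusion in section 5 is "Diabetes requiring the use of insulin".

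**The concern.** The crossover gives each subject a change in overnight FFA, in OGTT response and in RHI. The objective asks whether these changes move together. A regression of OGTT or RHI on FFA level, adjusted for age, sex and BMI, answers another question: whether people with higher FFA tend to have worse glucose tolerance or endothelial function. Someone with diabetes may have both higher FFA and a worse OGTT on both nights, whatever OSA does. Such a regression could report a downstream effect where the OSA-induced change has none, or misstate the size of a real one.

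This is the analysis that would connect FFA to cardio-metabolic harm, and the Abstract presents the study as a step towards judging FFA as a biomarker of that risk.

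**Working it through.** **1. The plan's own figure.** Under Sample Size, Δ FFA is 0.047 in men and 0.021 in women, SD 0.04 mmol/l.
- d = (0.047 − 0.021)/0.04 = 0.65.
- A two-sided two-sample t-test at 0.05 with 80% power needs 38.14 per group, so 39 per group, 78 in all.
- 78/(1 − 0.15) = 91.8, so 92 enrolled.

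The plan's figures reproduce. They concern the sex difference; no figure is given for the downstream analysis. I take 78 as the number of complete pairs.

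**2. How far level stands in for change (rough).** Weighted mean Δ FFA = (13 × 0.047 + 7 × 0.021)/20 = 0.038 mmol/l. With the stated median rise of about 8.9%, the level is near 0.038/0.089 = 0.43 mmol/l (this mixes a mean and a median). The variance of the change is 0.04² = 0.0016. If the between-person coefficient of variation of level is 20% (assumed), the level variance is (0.2 × 0.426)² = 0.00725 and the ratio is 22%. At 40% it is 0.0016/0.0290, about 6%. Level would mostly reflect stable differences between people.

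**3. False positives when FFA has no effect.** Simulation: 78 subjects, two nights, 3,000 trials per setting, test at 0.05. All of the following are assumptions, not in the documents: residual SD 1 for FFA and glucose, within-person correlation 0.7, and diabetes shifting both nights equally by the amounts shown in residual SDs. Level models adjust for age, sex and BMI.

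| Diabetes share; FFA/glucose shift | One night | Mean of both nights | Both nights pooled, no subject term | Change-on-change | One night plus diabetes |
|---|---|---|---|---|---|
| 10%; 0.5/1.0 | 7.0% | 7.9% | 16.5% | 4.7% | 4.9% |
| 20%; 0.5/1.5 | 14.0% | 17.2% | 31.3% | 5.2% | 5.1% |
| 30%; 0.75/1.5 | 35.2% | 44.6% | 62.1% | 5.1% | 4.2% |
| No diabetes effect | 5.4% | 4.8% | 10.7% | 5.0% | 5.7% |

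The first and third rows are the extremes of nine settings. Pooling is inflated even with no diabetes effect, mainly because two nights from one person are treated as independent.

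A second set of assumptions (between-person SD 0.8; night-to-night SD 0.4 for FFA and 0.5 for glucose; diabetes shifts of 0.3 to 0.8 in FFA and 1.5 in glucose; 10% to 30% diabetics) gave 7% to 50% for one night and about 5% to 6% for change-on-change.

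**4. When there is a true effect.** With a true slope of 0.30, 20% diabetics and shifts of 0.5/1.5, the one-night slope averaged 0.42 and the change-on-change slope 0.31. Power was 74% for change-on-change and 71% for one night adjusted for diabetes.

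**5. Where change-on-change also fails.** Suppose diabetes enlarges the response to withdrawal itself (assumed: 20% diabetics, extra response 0.3 to 0.5 in FFA and 0.3 to 0.8 in glucose, with night-to-night SDs as in the second set). Change-on-change without a diabetes term was then falsely significant in about 6% to 23% of trials. Adding diabetes brought this back to about 5%.

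**6. Power with 78 pairs.** Fisher z: power = Φ(atanh(r) × √75 − 1.96).
- r = 0.20: 42%
- r = 0.25: 60%
- r = 0.30: 76%
- r = 0.313: Φ(0.3239 × 8.660 − 1.960) = Φ(0.845) = 80%
- r = 0.40: 96%

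**The case against.** The strongest reply is that the sentence is incomplete, not wrong. It does not say which night is used, what the unit of analysis is, or whether the FFA profile is a level or a change. Its heading speaks of elevation, the responder bullet ties elevation to CPAP withdrawal, and Study Statistics says the Aim 2 analyses mainly concern heterogeneity during withdrawal. A reader might infer that the plan commits to a comparison across people and throws the crossover away. The documents do not support that; they leave the point open. Nor do the covariates settle it, because a regression of change on change may also adjust for age, sex and BMI.

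A reader might also infer that diabetes has been left out of the adjustment. The covariate list is given only as examples, and Sample Size describes its preliminary data as coming from non-diabetics, so the investigators do distinguish the groups. Adding diabetes alone restores about 5% in the one-night simulation.

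These replies limit the claim without removing it. Neighbouring bullets name a change or a subject effect and this one names neither, so an analyst following the text could reasonably run level on level. Adding diabetes deals with one stable trait; differencing deals with every trait that shifts both nights equally. It is also fair that this is a secondary association in a self-described pilot, and that the effect of withdrawal on glucose tolerance and endothelial function belongs to Aim 1.

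**Conclusion.** The concern holds as a mismatch between objective and written analysis. The objective is about change, the paired data to answer it are planned, and the analysis text does not call for their use. On its most natural reading it could present stable traits as a downstream effect of FFA.

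The size is not known. One-night inflation of 7% to 35%, and up to 62% for nights pooled without a subject term, rests on diabetes shares, shifts and correlations that the documents do not give. The direction is firmer: a level regression is open to any unadjusted stable trait related to both FFA and the outcome.

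The reach is limited to this one secondary analysis. The primary FFA comparison is a mixed model with subject ID as a random factor and is not touched. It should be corrected before analysis, but it does not threaten the main result.

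**What to change.** Name one main analysis for this objective, in either of two forms:
- Regress the NDS-minus-CPAP difference in OGTT measures, and separately in RHI, on the NDS-minus-CPAP difference in mean nocturnal FFA, with terms for visit order and diabetes status.
- Fit a two-night mixed model with subject ID that splits FFA into the subject's mean and the within-subject deviation, with condition, period and diabetes status. The within-subject coefficient is the answer. To match the first form, diabetes must also interact with condition; its main effect alone does not cover a larger response to withdrawal among diabetics.

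Keep any association of levels between people as descriptive, adjusted for diabetes. Describe the within-person result as an association too, because OSA may affect FFA and glucose by separate routes and differencing does not remove that.

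The cost is wording; the OGTT and EndoPAT are already planned after both visits. Diabetes status must be recorded, which screening for the diabetes exclusion should already provide. The downsides are that subjects missing a night contribute little to the within-person estimate, and that with 78 pairs a weak association may be missed (about 42% power at a correlation of 0.20). The plan should say so, so that a null result is not read as no link.

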Sample Size: One of the stated goals of this study is to examine sex-specific lipolytic responses to CPAP withdrawal. We base our sample size on the ability to detect a difference in FFA elevation between men and women. In the 20 non-diabetics of our preliminary data, the average Δ FFA during CPAP withdrawal was 0.047 ± 0.04 mmol/l in men (n=13), and 0.021 ± 0.04 mmol/l in women (n=7). This yields a medium effect size (Cohen's $d = 0.65$). To detect a sex difference at 80% power at a significance level of 0.05, requires a sample size of 78 (39 men and 39 women). We anticipate potential technical problems (e.g. IV failures, hemolysis, and poor sleep efficiency) leading to loss of 15% data. Therefore, our target enrollment will be 92 subjects.

Early stopping rule

At any point in the study, the subject may decline to participate. Indications for stopping are the development of severe adverse events. The DSMB and IRB will be informed of any adverse events. Any serious adverse events will result in study discontinuation.

7. Risks

- a. Medical risks, listing all procedures, their major and minor risks and expected frequency.

Venipuncture: May be associated with discomfort and bruising. Infection or irritation (phlebitis) can occur at the IV site.

Phlebotomy: In total, the blood collected will be approximately 174 cc (as compared to approximately 350 mL during a donation). Theoretically, if too much blood is lost, this could lead to low blood pressure and cardiovascular stress or dizziness.

Withdrawal of CPAP: During abstinence from CPAP over 3 days, subjects may experience relatively unrefreshing sleep. During the night, they may experience arousals from sleep, morning headache. During the daytime, they may experience subjective and/or objective daytime sleepiness. The risk of sleepiness contributing to an accident such as work-related injury or motor vehicle collision is also increased. Chronically, OSA is associated with increased risks of hypertension, diabetes, stroke, and ischemic heart disease. In a recent study on the effects of 2-weeks of CPAP withdrawal, there were modest and gradual increases in daytime blood pressure, heart rate, and triglycerides⁷. Risks of stopping CPAP for 2 weeks is therefore a low-risk, high yield research method. In this study, withholding CPAP for a few days is associated with even fewer risks.

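### The 80% power for the sex comparison rests on non-diabetics only, but diabetics not on insulin are eligible and the powered t-test takes no account of diabetes

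*Combined protocol and SAP*

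**What the plan says.** - **Study Statistics, Sample Size.** The size is set by the sex contrast: "We base our sample size on the ability to detect a difference in FFA elevation between men and women". The planning values come from a subset, "In the 20 non-diabetics of our preliminary data": "0.047 ± 0.04 mmol/l in men (n=13), and 0.021 ± 0.04 mmol/l in women (n=7"). The plan derives d = 0.65 and says that 80% power at the 0.05 level "requires a sample size of 78 (39 men and 39 women"). The only inflation is 15% for technical data loss, giving 92 enrolled.
- **Section 5, Exclusion Criteria, item 4.** The only diabetes exclusion is "Diabetes requiring the use of insulin". Diabetics managed by diet or non-insulin drugs are eligible.
- **Study Statistics, Specific Aim 2, sex-specific effects.** The first analysis is "comparing mean change in FFA level during CPAP withdrawal between men and women (unpaired T-test"). The second is a multivariable regression with sex and a sex-by-BMI interaction. The hypothesis mentions adjustment for OSA severity and fat distribution.
- **Other FFA models** (section 4, Data Analysis; Study Statistics, Aim 2). These name age, sex, BMI or fat measures, OSA severity, arousals, heart rate and catecholamines. Diabetes is not named anywhere as a covariate, stratum, subgroup or restriction of the analysis set.

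**The concern.** The sponsor took the effect and SD from non-diabetics, which suggests that diabetes was thought relevant to the FFA response. The distinction then disappears from both eligibility and analysis. Two things are at stake.

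1. **Scope of the power statement.** If eligible diabetics have a different sex difference or a more variable FFA response, the effect size in the enrolled mix is not 0.65, and the stated power does not describe the test that will be run.
2. **Confounding.** Sex cannot be randomised. If diabetes affects the FFA response and is more common in one sex, an unadjusted t-test attributes part of the diabetes effect to sex.

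**Working it through.** **Inputs from Study Statistics, Sample Size.** Mean change 0.047 in men and 0.021 in women; SD 0.04 (mmol/l); power 80%; alpha 0.05; data loss 15%. Sidedness is not stated.

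**Reproducing the plan.**
- d = (0.047 − 0.021)/0.04 = 0.026/0.04 = 0.65, so the ± 0.04 is an SD.
- Two-sided t-based solution: 38.14, rounded up to 39 per sex, total 78. A one-sided test would need 30 per sex, so the plan is two-sided.
- 78/0.85 = 91.8, so 92 enrolled.
- Power at 39 per sex is 80.9%. It reaches 80% at d ≈ 0.643, so there is almost no reserve.

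The plan's arithmetic is correct for the population that supplied the inputs.

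**Dilution (assumptions).** Let p be the share of diabetics, equal in both sexes, and k their sex difference as a fraction of 0.026. Keep the overall SD at 0.04. Then d = 0.65 × [(1 − p) + p·k]. Two-sided t-test power at 39 per sex:

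| Share p | k = 1 (same response) | k = 0.5 | k = 0 (no sex difference) |
|---|---|---|---|
| 10% | d 0.650, 81% | d 0.618, 77% | d 0.585, 72% |
| 20% | d 0.650, 81% | d 0.585, 72% | d 0.520, 62% |
| 30% | d 0.650, 81% | d 0.553, 67% | d 0.455, 51% |

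In the other direction, with p = 20% and k = 1.25, d = 0.65 × (0.8 + 0.25) = 0.683 and power is about 85%.

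Holding the SD at 0.04 is a simplification. If k differs from 1, diabetic and non-diabetic means must differ in at least one sex, which adds a little variance. With the gap split evenly between the sexes, this lowers the k = 0 column by about one point or less.

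**Larger SD only (assumption).** With the difference kept at 0.026, an overall SD of 0.045 gives 71% power and 0.05 gives 62%.

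**Restriction to non-diabetics, d = 0.65.** With 10%, 20% or 30% of the 78 diabetic, 35, 31 or 27 per sex remain. Power is 76%, 71% or 65%.

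**Confounding (assumptions).** Bias in the unadjusted sex difference = (mean shift in FFA response due to diabetes) × (difference in diabetes prevalence between the sexes).
- Shift 0.02, prevalence gap 10 points: 0.02 × 0.10 = 0.002, or 8% of 0.026.
- Shift 0.04, prevalence gap 20 points: 0.04 × 0.20 = 0.008, or 31% of 0.026.

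The bias can go either way.

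**The case against.** The strongest reply is that no loss of power has been shown. The documents give no diabetic share, mean, SD or sex difference. If diabetics respond as non-diabetics do, 78 and 92 stand; if their sex difference is larger, power rises. This is right, and it is why the no-change case belongs in any range that is reported. A reader might infer that the trial is underpowered or that 92 must be raised. The documents do not support either inference.

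A second reply is that a diabetes covariate would not recover the dilution. This is also right. A smaller sex difference in diabetics is an interaction, and with diabetes balanced by sex an additive term leaves the sex estimate unchanged. The covariate deals with imbalance and with a mean shift; only the comparison within non-diabetics deals with dilution.

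Third, the planned regression has no closed covariate list, so diabetes could be added. It could, but that would not be prespecified, and the t-test that matches the sample-size calculation cannot include it.

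Fourth, this is an Aim 2 analysis in a study that calls itself a pilot, and d = 0.65 from 13 men and 7 women is very imprecise (approximate 95% CI −0.30 to 1.58). That limits the weight of the point. Yet this comparison alone sets the sample size, and imprecision in d is no reason to leave its population unstated.

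**Conclusion.** The point holds as a mismatch of populations. The effect size, SD and 80% power describe non-diabetics; eligibility admits diabetics not on insulin; and neither analysis of the sex difference names diabetes. These facts rest on the text alone.

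The size of the consequence rests on assumptions. Over shares of 10% to 30% and a diabetic sex difference between none and the same, with the SD unchanged, power runs from 51% to 81%. Values above 81% are possible if diabetics show the larger sex difference. Possible confounding of 8% to 31% of the planned difference depends on an assumed shift and prevalence gap.

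A reader might extend the point to the Aim 1 comparison of CPAP and OSA nights. The documents do not support that: the contrast is within subject, with subject as a random factor, and diabetes status is constant within a subject. A diabetes main effect would change it essentially not at all.

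**What to change.** 1. Replace the unadjusted t-test as the main sex comparison with a linear model for change in FFA on sex plus diabetes status. Define diabetes from history and medication before the study nights. A history is already taken, and the exclusion criteria already require asking about insulin and other drugs. Do not use the study OGTT: section 2 hypothesises that CPAP withdrawal impairs glucose tolerance, so the OGTT is an outcome, and the two visits could classify the same person differently.
2. Prespecify the same sex comparison in non-diabetics. This is the analysis that addresses dilution and matches the planning data.
3. State in the Sample Size paragraph that d = 0.65 and 80% power apply to 78 evaluable non-diabetics. Give an assumption-based range for the enrolled mix, including the no-change case. Any diabetic data in the preliminary study could narrow it.

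No diabetes term is needed in the Aim 1 contrast. The cost is analysis-plan wording, one degree of freedom and a less favourable power statement. No new data or participants are required.
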